¹² Lundh, L.G., Wangby-Lundh, M., & Bjarehed, J. (2008). Self reported emotional and behavioral problems in Swedish 14 to 15-year-old adolescents: A study with the self-report version of the Strengths and Difficulties Questionnaire. *Scandinavian Journal of Psychology*, 49, 523–532.

¹³ <https://youthinmind.com/products-and-services/sdq/>

¹⁴ Scoring the Strengths & Difficulties Questionnaire for age 4-17. (2014).

<https://www.ehcap.co.uk/content/sites/ehcap/uploads/NewsDocuments/236/SDQEnglishUK4-17scoring-1.PDF#page=4>

¹⁵ Goodman A, Lamping DL, Ploubidis GB. When to use broader internalising and externalising subscales instead of the hypothesised five subscales on the Strengths and Difficulties Questionnaire (SDQ): data from British parents, teachers and children. *J Abnorm Child Psychol*. 2010 Nov;38(8):1179-91. doi: 10.1007/s10802-010-9434-x. PMID: 20623175.

¹⁶ Van den Broeck, A., Vansteenkiste, M., De Witte, H., Soenens, B., & Lens, W. (2010). Capturing autonomy, competence, and relatedness at work: Construction and initial validation of the Work-related Basic Need Satisfaction scale. *Journal of Occupational and Organizational Psychology*, 83(4), 981-1002.

¹⁷ Stanton, J. M., Balzer, W. K., Smith, P. C., Parra, L. F., & Ironson, G. (2001). A General Measure of Work Stress: The Stress in General Scale. *Educational and Psychological Measurement*, 61(5), 866–888. <https://doi.org/10.1177/00131640121971455>

more stress. The sixth secondary outcome measure is the mean of the responses for the 8 items¹⁸ where “no” is coded as 0, “?” is coded as 1.5 and “yes” is coded as 3 (2vi)¹⁹.

2iv) Days attended

The hypothesised lower stress may lead to fewer sick days of social workers. We measure this over the entire intervention period from T1 to T13. Instead of measuring the number of sick-days, we will instead measure the number of ‘days attended’ in work. This allows us to include social workers who leave their posts over the course of the trial - these individuals will be classified as absent every day after they leave. Excluding these participants from the absence analysis would risk biasing the results, as individuals’ likelihood to leave is correlated with their rate of sickness absence. The number of days not attended may include holidays and parental leave in addition to sickness absence. If possible, we will control for the number of days of holiday and parental leave.

Foster and kinship Carer Outcomes

2v) Self-efficacy

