- For each outcome, we will regress an indicator of missingness on the covariates in the main model (see the “Covariates” section) using logistic regression with standard errors clustered at the team level. If any of the coefficients on the covariates of the missingness model are statistically significant at the 5% level, then data is not missing completely at random (MCAR).
- In particular, we are interested in the coefficient on the treatment dummy. If it is not significant, this suggests that the data is missing experimentally at random (MEAR) (where data may be correlated with observable or unobservable variables, but not with treatment assignment) and we will only include observations for which we have the outcome data controlling for any variables which are significant (if they are not already specified in the “Covariates” section above).
- In line with WWCS statistical guidance, if the data on outcomes is missing experimentally not at random (MENAR) e.g. due to large differential attrition, then we will multiply impute within the treatment condition.

Sensitivity analysis following multiple imputation

Given that there may be a substantial proportion of outcome data to impute, we check the sensitivity of our results to the imputation strategy. We will:

²¹ See Taljaard, M., Donner, A., & Klar, N. (2008). Imputation strategies for missing continuous outcomes in cluster randomized trials. *Biometrical journal. Biometrische Zeitschrift*, 50(3), 329–345. <https://doi.org/10.1002/bimj.200710423>

- impute using baseline observation carried forwards (BOCF)
- impute using control drifted observation carried forward (CDOCF). This is done by carrying forward the baseline observation and then adding the “drift” from the comparator group to take into account the amount their outcome would have changed in the absence of treatment. The drift is calculated using an autoregression model for the comparator group.

Reporting

In addition to handling missing data and conducting sensitivity analyses, we also report some summary statistics to allow for a qualitative assessment of the impact of missing data on the treatment effect estimate.

- For each outcome and covariate, we will report the percentage of missing data alongside summary statistics
- Rates of loss to “post” data collection for the arms of the trial

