- A table of baseline characteristics broken down by treatment arm and response to “pre” data collection and response to “post” data collection (including both those who remained in the sample and those who joined) to check whether characteristics have become more imbalanced by “post” data collection.
- Missing data is likely to be most problematic for data collected via primary data collection (vs routinely collected data). For the outcomes collected via routinely collected data, we will add in an indicator of missingness in the primary data collection and an interaction term between treatment and missingness in the primary data collection. The interaction term can be interpreted as the additional treatment effect on those who are missing from the primary data collection. This gives some proxy as to the likely direction and magnitude of attrition bias for the outcomes collected in the primary data collection.

Reporting

Some of the statistics we will report have been mentioned in earlier sections but we gather them here for ease of reference:

- For each outcome and covariate, we will report the percentage of missing data alongside summary statistics
- Rates of loss to “post” data collection for the arms of the trial
- A table of baseline characteristics broken down by treatment arm and response to “pre” data collection and response to “post” data collection (including both those who remained in the sample and those who joined)
- Description of sites (to allow for qualitative assessment of generalisability of findings)
- ICC at the team level (pre and post for all outcomes)
- Direction and standard errors of the site-treatment effects

Implementation and process evaluation

Aims

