Pseudonymised administrative data on interactions with children's social care (CIN plans, CPP, CLA and case closure) will be requested from local authorities. Consent for the sharing of this data will not be explicitly sought from families. This is because we consider the risk to participants arising from the sharing and processing of this data for the purpose of the evaluation to be very low, and the benefit to accessing the data for all eligible participants to be high. The risk that the eligible participants are identified is very low, and the risk of a data breach will be carefully managed so that it remains low. The benefit of accessing the data for all eligible participants is that we maintain statistical power and reduce the risk of selection bias into the sample, allowing for better - unbiased and more precise - estimates of the treatment effect, making the evaluation much more useful to decision-makers. Having said this, participants will be able to withdraw their consent for their data to be processed for the evaluation if they so choose to via a form on the WWCS website. Please see the Data Protection section below for more details on the data governance of this.

Social workers and family support workers

Pseudonymised administrative data on the sickness absence of social workers and family support workers will be requested from local authorities. Consent for the sharing of this data will not be explicitly sought from social workers for the same reasoning as above.

Summary statistics about access to Kitbag Online will be requested from IFF. Given that the social worker participants will not have accessed the website before, it may be possible to add consent to share for purposes of the evaluation into the terms of use. We are currently investigating this with the delivery partners.

Implementation and process evaluation

Focus group discussions and interviews

Focus group discussion and Interview participants will be sent an information sheet in advance of the interview. Before the interview commences, the researcher will ask the participant if they have read and understood the information sheet, and whether they have any questions. The researcher will then elicit consent for participation and for the interview to be recorded. When eliciting consent for participation in interviews, researchers will make clear the limits of confidentiality (See Section D for further information).

Observation

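### The outcome-missingness step can never add a control and tests response rates, not who responds; the staff absence record enters no stated adjustment of the stress and self-efficacy estimates

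*Protocol*

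**What the plan says.** Protocol, Missing data strategy, Outcomes: for each outcome, "we will regress an indicator of missingness on the covariates in the main model", by logistic regression clustered on team. Any covariate coefficient that is "statistically significant at the 5% level" rules out missing completely at random. The treatment coefficient then decides the route.

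- **Not significant:** the data are treated as missing experimentally at random, and "we will only include observations for which we have the outcome data controlling for any variables which are significant". A parenthesis limits the added controls to variables "if they are not already specified in the" Covariates section.
- **Missingness judged related to treatment:** "then we will multiply impute within the treatment condition", followed by two carry-forward sensitivity analyses.

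For staff outcomes, the Covariates section lists gender, role, contract type, experience, team characteristics, site and the earlier value of the same outcome. Absence is not listed for stress or self-efficacy.

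Absence appears in three other places.

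- Consent procedures: "Pseudonymised administrative data on the sickness absence of social workers and family support workers will be requested from local authorities", without explicit consent being sought.
- Secondary outcome 2iv (days attended): lower stress is expected to reduce sick days, and a worker's "likelihood to leave is correlated with their rate of sickness absence".
- Reporting, within the missing data strategy: for routinely collected outcomes, "we will add in an indicator of missingness in the primary data collection", plus its interaction with treatment, as a rough guide to attrition bias in the survey outcomes.

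**The concern.** Worker stress and self-efficacy are measured by online survey. The Data collection schedule assumes a 10% response, and the protocol expects about 20% of staff to have left by T13. At that level of loss, the credibility of these two estimates rests on how non-response is examined and handled.

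The stated check has two weaknesses. Its provision for extra controls cannot operate. Its deciding test compares how many respond in each arm, whereas bias in the treatment effect comes from who responds. Two arms can have identical response rates while one loses its most strained workers and the other does not. The plan would then analyse respondents only and add no control.

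The protocol holds a variable that bears on this. Absence data do not depend on answering the survey, the protocol ties absence to stress and to leaving, and it names leaving as a cause of survey loss.

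**Working it through.** No figure in the protocol is at issue, so there is none to reproduce. The check has two parts.

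**1. What can the step add?**

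- Candidates: the predictors in the missingness model, which are treatment plus the main-model covariates.
- Exclusions: everything already in the Covariates section, which is the same list.
- Candidates minus exclusions: the empty set, for every outcome.
- With the absence record in the missingness model, one variable would become available.

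The earlier stress or self-efficacy score may also be lost. The protocol drops any covariate with more than 30% missing. At 10% response the T6 score would be about 90% missing, if missingness is counted over all eligible staff (my assumption).

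**2. How large could the bias be?**

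The inputs are assumptions except the 10% response. Stress *y* and absence *a* are standardised, there is no true effect, and corr(*y*, *a*) = *r* = 0.3 or 0.5. Response follows logit P(R) = c + g·*a*, with g set separately by arm and c chosen so that **both arms respond at 10%**. The treatment test then has no difference in rates to find.

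Since response depends on *a* only, E(*y* | R) = r · E(*a* | R), so

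bias = r · [E(*a* | R, intervention) − E(*a* | R, control)],

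where E(*a* | R) = ∫ a·p(a)·φ(a) da / ∫ p(a)·φ(a) da. Numerical integration gives 0 for g = 0, −0.440 for g = −0.5, −0.601 for g = −0.7 and −0.817 for g = −1.0.

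| g, intervention | g, control | Bias, r = 0.3 | Bias, r = 0.5 |
|---|---|---|---|
| −0.5 | −0.5 | 0 | 0 |
| −1.0 | −1.0 | 0 | 0 |
| −0.7 | −0.5 | −0.05 | −0.08 |
| −1.0 | −0.7 | −0.06 | −0.11 |
| −0.5 | 0 | −0.13 | −0.22 |
| −1.0 | 0 | −0.25 | −0.41 |

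For example, 0.5 × (−0.817 − 0) = −0.41 SD. The negative sign is a spurious reduction in stress; it reverses if the dependence sits in the control arm.

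**With absence used by arm.** In each arm the respondents' regression of *y* on *a* recovers slope r and intercept 0. Averaged over all staff in the arm, it gives a mean of 0, so the bias is about 0 in every row.

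**If response depends on stress itself** (g = −0.5 or −1.0 in the intervention arm only, same intercept in both arms): bias is −0.44 to −0.77 SD without absence and −0.33 to −0.71 SD with it. Absence removes roughly 8 to 24%.

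**In-trial absence as an ordinary covariate.** In a separate simulation the true effect was −0.200, dependence was equal in both arms and r was 0.2 to 0.6. Respondents-only estimates were −0.192 to −0.202. Adding in-trial absence to the outcome regression pulled the estimate to between −0.141 and −0.193.

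**The case against.** The strongest reply is that the plan is not blind to this. The Reporting diagnostic relates survey non-response to routine outcomes, with an interaction by arm. For staff the routine outcome is days attended, so a different link between absence and response in the two arms is what that interaction would show. This stands, and a reader who inferred that the absence record is ignored would be wrong. But the diagnostic neither changes the choice of route nor adjusts any estimate. Days attended also counts leavers as absent every day after they go, which mixes sickness with departure.

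A reader might also infer that the imputation route merely reproduces the respondents-only estimate. That would follow if only the analysis covariates were used and only the outcome were missing. The protocol does not list the imputation model's contents, and a SAP may. The carry-forward analyses on that route would not reproduce it either. I do not claim that both routes give the same answer.

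The larger biases need dependence in one arm only, and nothing in the protocol shows this. Some difference is plausible because only intervention staff are asked additional questions about Kitbag use, but its size is unknown.

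Finally, a clean sickness rate may not be obtainable. Days not attended may include holidays and parental leave, which the protocol will control for only if possible. The model would also rest on few respondents: about 30 of the 300 intervention staff in Table 2 at 10%.

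**Conclusion.** The point holds in a limited form. It is certain from the text that the add-a-control clause is empty and that the missingness model holds nothing beyond the main-model covariates. It is also certain that a test of the treatment coefficient cannot see arms that differ in who responds.

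The consequence for the stress and self-efficacy estimates is conditional on the assumed 10% response and correlation of 0.3 to 0.5. Bias is about 0 with equal dependence on absence, 0.05 to 0.11 SD with modestly different dependence, and 0.13 to 0.41 SD with dependence in one arm only. It is mostly not removable through absence if stress itself drives response.

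The documents do not show that such bias will occur. The primary outcome, children's social care involvement, is administrative and is not affected by survey non-response. This is a worthwhile improvement to two secondary outcomes, not a flaw in the trial's main result.

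**What to change.** For worker stress and self-efficacy:

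1. Add sickness absence while in post to the outcome-missingness model, for the pre-trial period and for T1 to T13, as far as the records separate it from other leave.
2. Use the same variables as auxiliary predictors in imputation within arm, or in response weights. Report that result beside the respondents-only result, whichever way the treatment-coefficient test falls.
3. Keep T1 to T13 absence out of the outcome regression. It is post-randomisation and hypothesised to follow from stress.
4. Delete the clause on controlling for significant variables not already specified, or name the additional candidates it is meant to cover.

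The cost is some wording and a modest amount of analysis. In-trial absence data are already requested, and the protocol expects earlier values of administrative measures to be available. The drawback is a slightly larger model fitted on few respondents, so no auxiliaries beyond these should be added. The report should state that the adjustment does not protect against response driven by stress itself.

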- for social workers and family support workers: the social worker or family support worker was a member of a team assigned to the intervention at point of randomisation and 0 else;
- for foster / kinship carers: the carer cares for a child or young person whose case is held at the point the foster carer enters the sample, by a social worker who is a member of a team assigned to the intervention at point of randomisation and 0 otherwise.

Although there is some turnover of social workers, family support workers and foster carers, about 80% of those at T0 (April 2021) will still be working with the local authority at T13 (May 2022), and so 80% will have received the full 12 months of the intervention. Binarising the treatment seems a reasonable proxy in this case.

For the outcomes relating to children, treatment is coded as a binary variable. When children enter the sample, at either the point of randomisation, or the point they become eligible (e.g. their case opens and meets other criteria) they will be allocated to treatment if the team of their allocated social worker was randomised to treatment.

Covariates

Including control variables increases the precision of the estimate. In each regression, we control for a number of relevant covariates. We outline different categories of covariates below.

Site effects

We include site fixed effects but not site-treatment interaction terms.

Previous outcome measures

We control for the previous measurements of the outcome variable where data is available. For the survey-based measures for social workers, family support workers and foster carers, the same measures will be asked at T6 (October 2021) and T13 (May 2022), and for administrative data we expect previous values to be available. For the outcomes of the CYP and parents / carers (including kinship carers), the previous measure of the outcome will be at T0 (April 2021) or when they entered services if they entered services after T0 (April 2021).

Other covariates

For CYP outcomes (primary outcome i) and secondary outcome i)), we include the following vector of individual-level covariates:

- gender (coded as male, female, or other/missing)
- age group (4-11, 12-17, 18 years, or missing with 4-11 as the reference category)
- ethnicity (Asian / Asian British, Black / African / Caribbean / Black British, Mixed / Multiple ethnic groups, Other ethnic group, White, missing; with the majority group as the reference category)

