Missing post-intervention data is a risk for this trial as some of the secondary outcomes are collected via primary data collection (an online survey) and the attrition is likely to be high given that the follow-up period is over a relatively long period of time (4 months - 12 months later) and the professionals may have left their employer.

Covariates

- If the covariate has more than 30% of the data missing, we will drop the covariate.
- For each covariate in the main model (see the “Covariates” section) that has up to 30% of the data missing, we will regress an indicator of missingness on the other covariates in the main model and outcomes using logistic regression, clustering the standard errors at the team level. If any of the coefficients on the covariates of the missingness model are statistically significant at the 5% level, then data is not missing completely at random (MCAR).
- To distinguish between whether the data is missing at random (MAR) i.e. missing conditional on observables or missing not at random (MNAR) i.e. missing conditional on unobserved variables, for all the covariates that were not MCAR we then impute the missing values of the covariate of interest (using a missing category for categorical variables and multiple imputation for numeric variables) and compare the treatment estimates using the imputed data and data restricted to the complete cases. If the results are similar (i.e. significant / insignificant, the same direction and only differing in magnitude of up to 20%), then data is likely to be missing at random (MAR). If the results are dissimilar, the data is likely to be missing not at random (MNAR).

If the data on covariates are MCAR or MAR, then complete case analysis is likely to be unbiased but less well powered. To maintain power we use a missing category for categorical variables as missingness is likely to be a predictor in itself and multiply impute missing numerical covariates (including pre outcome measures). We ignore the clustered structure of the data because cluster sizes are small, cluster follow-up rates may be highly variable and we expect the ICC to be low (we assume the ICC to be 0.03 in power calculations)²¹.

Outcomes

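### The only two sensitivity analyses of imputed outcomes, BOCF and CDOCF, are fixed single fills that distort the estimate or its standard error when loss differs by arm, so they say little about robustness

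*Protocol*

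**What the plan says.** The protocol's missing data strategy expects loss in the online surveys; it says "the attrition is likely to be high given that the follow-up period is over a relatively long period of time". For outcomes it regresses missingness on the covariates. If the treatment coefficient is not significant, only observed outcomes are analysed. If missingness does depend on arm, "then we will multiply impute within the treatment condition".

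The subsection on sensitivity analysis following multiple imputation then opens: "Given that there may be a substantial proportion of outcome data to impute". It names two checks. The first is to "impute using baseline observation carried forwards (BOCF"). The second is to "impute using control drifted observation carried forward (CDOCF"), which takes the earlier measure and adds the comparator arm's change: "The drift is calculated using an autoregression model for the comparator group". No residual draw, repeated imputation or variance correction is described for either.

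The covariates section puts the same earlier measure in the outcome regression: "We control for the previous measurements of the outcome variable where data is available". For the survey outcomes that measure is the T6 survey.

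**The concern.** A value filled in from the earlier score lies on, or close to, a line in a covariate that the model already contains. It brings no information about the treatment contrast, yet the regression counts it as an observed outcome. Each method also imposes a single assumption about non-respondents and does not vary it.

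The place of these checks makes this matter. They follow the multiple-imputation branch, which is entered when loss is related to arm. The question there is how far the survey results (staff self-efficacy and stress, carer self-efficacy) depend on what non-respondents would have reported. If the checks move for mechanical reasons, a reader may take a shift as evidence of fragility, or agreement as evidence of robustness, when neither follows.

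**Working it through.** **Inputs.** The protocol gives no figure for these sensitivity analyses and no missing rate for the survey outcomes. Its one design figure, the MDES of 0.127, concerns the child outcome and is not in question. It expects that "about 80% of those at T0 (April 2021) will still be working with the local authority at T13 (May 2022"), so about 20% of staff and carers leave, with survey non-response on top. Assumed here: 300 people (150 per arm), correlation r = 0.6 with the earlier measure, no clustering, outcomes in SD units, true effect d of 0.30 or 0. The residual variance is 1 - 0.36 = 0.64. Write m0 and m1 for the missing shares in control and intervention.

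**CDOCF, estimate.** Control fills lie on the control line and leave it unchanged. Intervention fills lie on the same line and carry no effect. The estimate is therefore about (1 - m1) x d:
- 30%/50% missing: 0.50 x 0.30 = 0.15.
- 50%/30% missing: 0.70 x 0.30 = 0.21.

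**CDOCF, standard error.**
- Actual variance: (1 - m1)^2 x 0.64 x [1/(150(1 - m1)) + 1/(150(1 - m0))].
- Variance reported by OLS on the filled data: about 0.64 x (1 - average missing share) x 2/150.

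All three cases below average 40% missing, so the reported SE is sqrt(0.64 x 0.6 x 2/150) = 0.072 throughout.

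| Control / intervention missing | Actual SD, formula | Reported SE, formula | Simulation: SE vs SD |
|---|---|---|---|
| 40% / 40% | sqrt(0.36 x 0.64 x (1/90 + 1/90)) = 0.072 | 0.072 | 0.072 vs 0.074 |
| 30% / 50% | sqrt(0.25 x 0.64 x (1/75 + 1/105)) = 0.060 | 0.072 | 0.073 vs 0.063 |
| 50% / 30% | sqrt(0.49 x 0.64 x (1/105 + 1/75)) = 0.085 | 0.072 | 0.072 vs 0.085 |

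The formula ignores the effect itself and chance variation in the number missing, which accounts for the small differences. In the last row a nominal 5% test uses a cut-off of 1.96 x 0.072/0.085 = 1.66 true SDs, which gives about 10% rejection under no effect. Simulation also gives 10%.

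**BOCF.** Relative to the earlier score, the intervention mean moves by (1 - m1)(drift + d) and the control mean by (1 - m0) x drift. The difference is (1 - m1) x d - (m1 - m0) x drift.
- No effect, 30%/50% missing, drift -0.3 SD: -(0.2)(-0.3) = 0.06. With an SE of about 0.076 this is 0.79 SEs, so rejection is about 12%. Simulation gives 0.06 and 13%.
- No drift: the formula reduces to (1 - m1) x d, which is shrinkage only.

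**Check with clustering.** A second simulation used 60 teams of 10 staff (team size assumed), ICC 0.03, team-clustered SEs and an effect of 0.25. With r = 0.894, from the R-squared of 0.8 in the MDES section:
- The CDOCF SE was 0.035 against an SD of 0.031 at 15%/35% missing, and 0.035 against 0.041-0.042 at 35%/15%.
- BOCF gave 0.27 at 35%/15% with drift +0.3 SD; the formula gives 0.85 x 0.25 + 0.2 x 0.3 = 0.27. At 15%/35% with drift -0.6 SD it gave 0.28; the formula gives 0.65 x 0.25 + 0.2 x 0.6 = 0.28.
- Within-arm multiple imputation returned 0.25 in the same settings, with 93-95% coverage.

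With r = 0.73, no effect, 15%/35% missing and drift -0.3 SD, BOCF gave 0.06 with 17% rejection. Clustered SEs therefore do not remove the problem.

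**The case against.** Four points can be made for the plan.

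**Precision.** A reader might infer that the intervals are falsely narrow in general, because they are narrower than if everyone had answered. With balanced loss that is not so. At 40%/40% missing the SEs match the estimators' own variability (BOCF 0.076 vs 0.077, CDOCF 0.072 vs 0.074), and rejection under no effect is about 5%. The low coverage of a true 0.30 (64% and 61%) comes from the estimate moving to 0.18. Balanced loss would also mostly go to the observed-outcome branch, where these checks do not run. This point stands.

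**Direction.** A reader might infer that both methods always shrink the effect. That is true of CDOCF but not of BOCF, which can inflate an effect or create one when unequal loss meets a time trend.

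**Purpose.** CDOCF can be read as a deliberate scenario in which intervention-arm non-respondents gain nothing. That is a legitimate scenario, and shrinkage is then intended. It does not rescue the standard error under unequal loss, and it remains one fixed point instead of a range.

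**Other provisions.** The missing-data reporting section adds a treatment-by-survey-missingness interaction for the administrative outcomes, loss by arm, and baseline tables by response. These are useful, but they do not vary the imputed survey values.

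Whether CDOCF draws residuals could be settled in a statistical analysis plan that is not at hand. The protocol describes no draw.

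**Conclusion.** The concern holds within limits. In the branch where the checks mainly run, CDOCF shrinks the estimate by about the intervention arm's missing share, and its SE is too large or too small according to which arm loses more. BOCF mixes the effect with differential loss times drift. Neither agreement nor disagreement with the multiple-imputation result says much about robustness.

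The sizes rest on assumed sample size, correlation, missing shares and drift, since the protocol gives none for the survey outcomes. The two closed-form estimates do not depend on the assumed sample size or correlation.

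The reach is limited to a conditional sensitivity analysis of secondary outcomes. A reader might infer that the primary result is at risk. The documents do not support that, because the primary outcome comes from administrative records for all eligible children. The point should be corrected before analysis, but it does not threaten the trial's main conclusion.

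**What to change.** Replace BOCF and CDOCF with delta-adjusted multiple imputation:
- Impute within arm as already planned.
- Shift the imputed values by amounts set separately for each arm over a pre-stated grid, for example -0.5 to +0.5 SD.
- Fit the planned model with team-clustered standard errors and combine the results by Rubin's rules.
- Report the shift at which the conclusion changes.

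If a scenario of no benefit in non-respondents is wanted, keep it as control-based multiple imputation instead of a single fill.

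The cost is revised wording and a small amount of code on an imputation that is already planned. The downsides are that a shift range must be chosen and justified in advance, and that the intervals will be wider.
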